11.3.1. Reporting of Serious Adverse Events to Regulatory Authorities

The Sponsor (and/or designee) is responsible for submitting expedited reports of suspected and unexpected serious adverse reactions (SUSARS) to the appropriate regulatory authorities. All investigators participating in ongoing clinical studies with the study drug will be notified by the Sponsor (or designee) of SUSARs. SUSARS must be communicated as soon as possible to the appropriate IRB/IEC by the investigator, as applicable and/or reported in accordance with local laws and regulations. Investigators should provide written documentation of IRB/IEC notification for each report to the Sponsor.

SAEs that are anticipated to occur in this patient population will be collected and reported by the investigator as described in [Section 11.3](#). However, these events will not be submitted to the regulatory authorities as expedited reports unless they meet SUSAR criteria. These events that are considered to be exempt from expedited reporting include the following clinical endpoints:

- CV death
- Nonfatal MI
- Nonfatal stroke
- Unstable angina requiring hospitalization
- Coronary revascularization
- Heart failure requiring hospitalization
- Noncoronary arterial revascularization

11.3.2. Reporting of Patient Death

The death of any patient during the study, or within the 30-day follow-up period after they have completed the study (regardless of the cause), must be reported as detailed in [Section 11.3](#).

11.3.3. Reports of Pregnancy

Although not considered an SAE (unless the event occurs with a serious outcome), pregnancy information on female patients will be collected by the authorized safety designee. If a female patient becomes pregnant during the course of the study, study treatment should be discontinued immediately. The principal investigator or designee must complete and submit the Pregnancy Report Form within 24 hours of awareness of the pregnancy. In addition, patients who become pregnant will complete the Week 12/End of Study evaluations according to [Appendix 1](#). Whenever possible, pregnancies should be followed until outcome and the Pregnancy Outcome Reporting Form submitted to the safety designee once the outcome is known.

11.4. Adverse Events of Special Interest

Adverse events of special interest (AESI) include metabolic acidosis (clinical laboratories), hepatic, muscular (AE and CK evaluation), new onset diabetes/hyperglycemia, renal, cardiovascular, and neurocognitive/neurologic events. Based on previous experience with bemedoic acid, uric acid and hemoglobin will be closely monitored. Safety monitoring guidelines for hemoglobin are detailed in [Section 11.1.6.3.3](#). Specific monitoring guidelines are provided in the case of AEs uncovered through laboratory evaluations. Patients are to be queried at each study visit regarding changes in cognition and or signs/symptoms of hypoglycemia.

The protocol procedures included in the bempedoic acid clinical studies are part of standard clinical care for patients with elevated LDL-C and also address the potential and theoretic risks of bempedoic acid.

All bemedoic acid studies will include standard pharmacovigilance including evaluation of AEs, PE findings, vital signs, and laboratory assessments. Cardiovascular events will be adjudicated by an independent CEC in accordance with a prespecified charter. [REDACTED]

A high-contrast, black and white image showing a series of horizontal bars of varying lengths. The bars are set against a white background and appear to be composed of a grid of small squares. The bars are positioned in a staggered, non-overlapping manner, creating a sense of depth or a layered effect. The lengths of the bars decrease from left to right.

11.5. Data Monitoring Committee

An independent DMC will monitor unblinded accumulating patient safety and efficacy data until the last patient has completed study treatment. In addition, data on SAEs and deaths, including clinical endpoints, will be monitored by the DMC during this period. At each DMC review, relevant unblinded safety and efficacy information from ongoing studies of bempedoic acid will be provided to the DMC by an independent unblinded statistician and programmer. Additional details will be provided in a DMC Charter.

11.6. Clinical Event Committee

A blinded independent expert CEC will adjudicate designated clinical endpoints, including all MACE and non-MACE endpoints defined as: CV death (MACE), non-CV death (non-MACE), nonfatal MI (MACE), nonfatal stroke (MACE), hospitalization for unstable angina (MACE), coronary revascularization (MACE), non-coronary arterial revascularization (non-MACE), and hospitalization for heart failure (non-MACE) using standardized definitions. Any clinical endpoints that meet SAE criteria will be reported as SAEs.

11.7. Assessment of Lipid Endpoints

11.7.1. Lipid Parameters

Basic fasting lipid samples will be collected during Screening (Visits S1 and S3) and at the 4 double-blind treatment visits (Visits T1, T2, T3, and T4). Lipid assessments will be performed as follows:

- Calculated TC, LDL-C, HDL-C, non-HDL-C, and TG.
 - If TG exceeds 400 mg/dL (4.5 mmol/L) or LDL-C is \leq 50 mg/dL (1.3 mmol/L), direct measure of LDL-C will be conducted.

Additional fasting lipids and other biomarkers, including apoB and hs-CRP, will be collected at Visits T1 and T4.

11.7.2. Clinical Safety Laboratory Tests

Clinical Safety laboratory samples will be collected Screening (Visit S1) and at the 4 double-blind treatment visits (Visits T1, T2, T3, and T4).

Blood draws for lipids (and glucose) must meet the criteria below. If these criteria have not been met, these blood samples will NOT be collected. If these criteria can be met by rescheduling clinic visit to occur within 3 days, these blood samples will be collected at the rescheduled clinic visit only.

- Blood samples will be drawn after a minimum 10-hour fast (water is allowed)

Patients are encouraged to be in a seated position during the blood collection. Clinical laboratory parameters and tests will include those listed in [Table 4](#). Collection schedule and instructions are provided in the Clinical Laboratory Manual. A description of the sample collection, storage, and shipping as well as monitoring and management of abnormal laboratories are described in [Section 11.1.6](#).

When ECG, vital signs, and laboratory samples are to be collected at the same time point, ECG and vital sign measurements will precede laboratory sample collection.

Table 4: Clinical Laboratory Parameters (Lipids) and Cardiometabolic Biomarkers

Clinical Laboratory Test	Clinical Laboratory Test
Basic Lipid Parameters 
Total cholesterol (TC)Calculated low-density lipoprotein cholesterol (LDL-C)High-density lipoprotein cholesterol (HDL-C)Non-high-density lipoprotein cholesterol (non-HDL-C)Triglycerides (TG)	Other Parameters 
High-sensitivity C-reactive protein (hs-CRP)apoB

12. STATISTICS

12.1. General Considerations

The statistical analyses described in this section will be performed as further outlined in a separate Statistical Analysis Plan (SAP). The SAP will supersede the protocol in the event of any differences between the two documents in the plans for data analysis, and the protocol will be amended, if needed. The SAP will be included as an appendix in the clinical study report for this protocol.

12.2. Determination of Sample Size

The primary efficacy endpoint for this study is the percent change from baseline to Week 12 in LDL-C.

The sample size of 150 randomized patients in the bempedoic acid 180 mg group and 75 randomized patients in the placebo group is expected to provide more than 95% power to detect a difference of 15% in the percent change from baseline to Week 12 in calculated LDL-C between the bempedoic acid treatment group and the placebo group. This calculation is based on a 2-sided t-test at the 5% level of significance and a common standard deviation of 15 %. The sample size of 150 randomized patients in the bempedoic acid 180 mg group and 75 randomized patients in the placebo group gives a total study sample size of 225.

12.3. Analysis Populations

The Full Analysis Set (FAS), used for all of the efficacy analyses, is defined as all randomized patients. The FAS is also known as the intention-to-treat (ITT) set of patients. Patients in the FAS will be included in their randomized treatment group, regardless of their actual treatment.

The Safety Population (SP), used for all of the safety summaries, is defined as all randomized patients who received at least 1 dose of study medication. Patients in the SP will be included in the treatment group that they actually received, regardless of their randomized treatment.

12.4. Disposition, Demographics, and Baseline Characteristics

Disposition, including reason for withdrawal from the IMP or study, will be summarized by treatment group. Demographic information and patient characteristics including, but not limited to, gender, race, age, and baseline vital signs will also be summarized by treatment group.

12.5. Primary Efficacy Analysis

The primary efficacy endpoint is the percent change from baseline to Week 12 in LDL-C.

Baseline LDL-C is defined as the mean of the values from Week -1 (Visit S3) and predose Day 1/Week 0 (Visit T1). The primary efficacy endpoint will be analyzed using analysis of covariance (ANCOVA), with treatment group as a factor and baseline LDL-C as a covariate. The ANCOVA will be performed using the FAS, with patients included in their randomized treatment group regardless of the treatment they actually received. The details of the ANCOVA model and options to correct for unequal variances and group size will be described in the SAP.

Missing data for the primary endpoint will be imputed using a multiple imputation method that accounts for treatment adherence. A pattern mixture model (PMM) will be used to specify different imputation strategies depending on whether the patient is still on study treatment. Imputed datasets will be analyzed using ANCOVA with treatment as a factor and baseline LDL-C as a covariate. Approximately 200 imputed datasets will be created, with results from the analysis of each imputed dataset combined using Rubin's method. The least squares mean (LSM) and standard error (SE) will be provided for both treatment groups, along with the placebo-corrected LSM, its 95% confidence interval (CI), and associated p-value. A confirmatory analysis using observed data only will also be performed for the primary endpoint.

12.6. Secondary and Tertiary Efficacy Endpoints

Secondary efficacy endpoints are also of interest for this study, in terms of controlling the overall Type I error rate. A gatekeeping or stepdown approach will be used to test the primary efficacy endpoint and then specific secondary efficacy endpoints sequentially in order to preserve the study-wise Type I error rate. The sequence for the stepdown procedure in this study is as follows:

1. Test the primary efficacy endpoint: percent change from baseline to Week 12 in LDL-C
2. Test the percent change from baseline to Week 12 in non-HDL-C
3. Test the percent change from baseline to Week 12 in TC
4. Test the percent change from baseline to Week 12 in apoB
5. Test the percent change from baseline to Week 12 in hs-CRP

In this hierarchical testing structure, each hypothesis is tested at a significance level of 0.05 2-sided. Statistical significance at each step is required in order to test the next hypothesis. If the primary efficacy endpoint meets the criteria for statistical significance, then the percent change from baseline to Week 12 in non-HDL-C will be tested; and so forth.

For the remaining secondary efficacy endpoints (percent change from baseline to Week 12 in TG and HDL-C) and the tertiary efficacy endpoints, a significance level of 0.05 will be used; given the large number of remaining endpoints, the p-values for those endpoints will be considered descriptive.

In general, change or percent change in lipid parameters at a given time point will be analyzed using a similar ANCOVA model for the primary endpoint with treatment group as a factor and the relevant baseline as the covariate.

Baseline for non-HDL-C, HDL-C, TC, and TG is defined as the mean of the values from Week -1 (Visit S3) and predose Day 1/Week 0 (Visit T1). Baseline for apoB and hs-CRP is defined as the predose Day 1/Week 0 (Visit T1) value.

Each ANCOVA will be performed using the FAS, with patients included in their randomized treatment group regardless of the treatment they actually received. Same imputation method described for the primary endpoint will be used for the secondary endpoints included in the stepdown testing procedure, while only observed data analysis will be used for other secondary and tertiary endpoints. For each lipid parameter at each time point, the LSM and SE will be

provided for both treatment groups, along with the placebo-corrected LSM, its 95% CI and associated p-value.

The ANCOVA assumption of normality will be assessed. If non-normality of the data is found at any time point for any parameter, either the data will be transformed so that it is normally distributed or a nonparametric test will be considered instead of the planned ANCOVA.

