5.4.3. Tertiary Efficacy Endpoints

Tertiary endpoints include assessments of percent change and absolute change from baseline in lipid levels at the additional time points of Week 4 (T2) and Week 8 (T3).

1. Percent change from baseline to Weeks 4 and 8 in
 - a. LDL-C
 - b. Non-HDL-C
 - c. TC
 - d. TG
 - e. HDL-C
2. Absolute change from baseline to Weeks 4, 8, and 12 in LDL-C.

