6.5. Number of Patients

Approximately 225 eligible patients will be randomized 2:1 on Day 1 (Visit T1) to receive either bempedoic acid 180 mg (N = 150) or placebo (N = 75) for 12 weeks.

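### Week 12 absolute LDL-C change is analysed on observed data only, while percent change built from the same two values is imputed for all randomized patients

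*Protocol*

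**What the plan says.** Section 12.3 defines the analysis set: "The Full Analysis Set (FAS), used for all of the efficacy analyses, is defined as all randomized patients". Section 12.6 repeats that each secondary and tertiary ANCOVA uses this set.

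Section 12.5 deals with missing values for the primary endpoint: "Missing data for the primary endpoint will be imputed using a multiple imputation method that accounts for treatment adherence". The pattern-mixture model applies different imputation strategies according to whether the patient is still taking study treatment. The same section also plans a confirmatory observed-data analysis of the primary endpoint.

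Section 12.6 gives the stepdown secondaries (non-HDL-C, TC, apoB, hs-CRP) the same imputation. For everything else, "only observed data analysis will be used for other secondary and tertiary endpoints". By Sections 5.4.2 and 5.4.3 the rest includes Week 12 percent change in TG and HDL-C, and tertiary endpoint 2: "Absolute change from baseline to Weeks 4, 8, and 12 in LDL-C". P-values for these endpoints are labelled descriptive.

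The synopsis says that absolute and percent changes are analysed in a similar way on the FAS. It does not mention the observed-data restriction.

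**The concern.** Percent and absolute LDL-C change at Week 12 are two expressions of the same pair of measurements. The plan imputes one and not the other. A reader who wants the primary result in mg/dL will look up the absolute change and find an estimate from fewer patients, under a different assumption about those who are missing.

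The protocol's own procedures make it plausible that some missing values come from patients off drug. Under Sections 10.2.5, 10.2.6 and 10.3.1, patients who stop treatment and decline clinic visits are followed by telephone, which yields no lipid sample. The pattern-mixture model was chosen to separate these patients from those still on treatment, and the observed-data rule sets that distinction aside for the affected endpoints. What is at stake is how far the descriptive Week 12 results agree with the primary result, not the primary test itself.

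**Working it through.** **1. The plan's own figure.** Inputs from Sections 6.5 and 12.2: 150 and 75 patients, difference 15 points, SD 15, two-sided 5% t-test.

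- Standard error of the difference = 15 × √(1/150 + 1/75) = 2.12 points.
- Noncentrality = 15 / 2.12 = 7.07 with 223 degrees of freedom, giving power above 99.99%.

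This agrees with the statement that the sample size "is expected to provide more than 95% power to detect a difference of 15% in the percent change from baseline to Week 12". The point raised here does not bear on power.

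**2. The two endpoints share their data.** Let B be a patient's baseline LDL-C, Y the Week 12 value, P the percent change and A the absolute change.

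- P = 100 × (Y − B) / B and A = Y − B, so A = B × P / 100.

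Whether the imputation model fills in Y or P, A follows by arithmetic in each of the roughly 200 imputed datasets. Similarly, HDL-C = TC − non-HDL-C, and both terms on the right are already to be imputed at Week 12. Only TG needs an additional imputed variable.

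**3. Possible size.** The protocol gives no dropout or missing-data rate, so the rate d is an assumption, shown over a range. Suppose that the observed difference is 15 points, a share d of active patients has no Week 12 value, those patients truly respond like placebo, and missing placebo patients respond like other placebo patients. Then:

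- all-randomized difference = 15 × (1 − d)
- gap (observed minus all-randomized) = 15 × d
- gap if only half of the missing active patients are off drug = 15 × d / 2
- gap in mg/dL = baseline × 0.15 × d

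The protocol gives no mean baseline LDL-C. A range of 100 to 140 mg/dL is assumed. The entry limits in Section 7.1 (100 and 120 mg/dL at Week -5, 70 mg/dL at Week -1) are thresholds, not means.

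| d | All-randomized difference | Gap, all off drug | Gap, half off drug | Gap in mg/dL (all off drug) | SE, observed data |
|---|---|---|---|---|---|
| 2% | 14.70 | 0.30 | 0.15 | 0.30 to 0.42 | 2.14 |
| 5% | 14.25 | 0.75 | 0.38 | 0.75 to 1.05 | 2.18 |
| 10% | 13.50 | 1.50 | 0.75 | 1.50 to 2.10 | 2.24 |
| 15% | 12.75 | 2.25 | 1.13 | 2.25 to 3.15 | 2.30 |
| 20% | 12.00 | 3.00 | 1.50 | 3.00 to 4.20 | 2.37 |

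The SE column is 15 × √(1/n₁ + 1/n₂) with the same share d missing in both groups; at 10%, for example, 135 and 67.5 patients on average. If missing patients respond like observed ones, every gap is zero.

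**The case against.** The case for leaving the rule alone has real weight.

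- **Observed data are not completers.** A reader might infer that the observed-data results favour completers. The documents do not support that. Section 10.3.1 asks patients who stop treatment to keep attending visits with fasting lipids, Section 8.5.2 keeps poor adherers in the study, and patients are analysed as randomized whatever they took. Off-drug patients who return at Week 12 are included. Only those with no value are left out, and some of those may be unrelated to treatment, such as non-fasting samples not collected under Section 11.1.6.2.
- **The LDL-C results can be compared.** A reader might infer that percent and absolute change cannot be read together. Section 12.5 plans an observed-data analysis of the primary endpoint, which puts both on the same observed basis. The reverse is not available: no absolute LDL-C, TG or HDL-C result is planned on the imputed, all-randomized basis of the primary result.
- **Direction is not established.** That the absolute change would look better than the primary result holds only if missing active patients have lost the effect. For TG and HDL-C the protocol states no expected direction.
- **The tiering is coherent.** Imputation covers exactly the five endpoints under type I error control, and the other p-values are descriptive. The FAS statement can be read as defining who belongs to the set, with missing-data handling specified separately. On that reading Sections 12.3 and 12.6 need a clarifying sentence rather than correction of a flat contradiction.

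These arguments remove the stronger claims. They give no reason to impute one transformation of a value and not the other.

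**Conclusion.** The point stands as a minor inconsistency in a rule that the protocol itself fixes. Whenever a Week 12 LDL-C value is missing, the planned percent and absolute results describe different patients. The absolute change may be biased if those without a value are mainly off drug.

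Direction and size cannot be determined from the protocol. Under the assumption that every missing active patient responds like placebo, the gap runs from 0.3 points at 2% missing to 3.0 points at 20%, against a standard error of about 2.1 to 2.4 points. It halves if half of them are off drug and vanishes if they respond like the rest. The primary conclusion and the type I error control of the stepdown sequence are untouched.

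**What to change.** Change the sentence in Section 12.6 so that Week 12 absolute LDL-C change is derived from the same imputed datasets as the primary endpoint and combined by Rubin's method. Preferably apply the same imputation to Week 12 HDL-C and TG, and keep the observed-data results for all three as supportive. HDL-C should be obtained so that it agrees with the imputed TC and non-HDL-C. For endpoints left on observed data, report the number analysed, label the results as observed-data, and qualify the statement that each ANCOVA uses the FAS. Bring the synopsis into line.

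The cost is slightly more programming, since the imputation code and the imputed Week 12 LDL-C values are needed anyway, plus one additional imputed variable for TG. No extra patients, visits or samples are required.

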12.7. Safety Endpoints

The summarization of AEs will include only TEAEs. TEAEs and SAEs will be summarized by SOC, severity, and relationship to study drug for each treatment group. These AE summaries will include cumulative incidence (percent of patients experiencing the AE) and patient-year adjusted incidence rates. If appropriate, absolute and relative risk differences will be calculated using both cumulative incidence and incidence rates. Deaths, withdrawal from study treatment due to AEs, and withdrawal from the study due to AEs will each be summarized by treatment group.

Clinical safety laboratories, including hematology, blood chemistry, HbA_{1C}, fasting glucose, and urinalysis; PE findings; vital signs; ECG readings; and weight will be summarized by the value and by change from baseline in the value (where appropriate) at each postbaseline time point.

12.7.1. Hepatic Safety

For liver-associated enzymes and TB, the number and percent of patients with abnormal values for ALT, AST, and TB will be summarized. Hy's law criteria ($\geq 3 \times$ ULN for either ALT or AST, with accompanying $TB > 2 \times$ ULN [$\geq 2 \times$ ULN conjugated/direct] bilirubin will be used in patients with Gilbert's Disease]) in the absence of other known causes will also be applied to the data; any potential Hy's law cases will be listed separately.

12.7.2. Musculoskeletal Safety

AEs of muscle-related symptoms will be summarized by treatment group. In addition, the number and percent of patients with abnormal CK values will be summarized.

12.7.3. Diabetes and Hyperglycemia

Cases of worsening and new onset of diabetes will be recorded as AEs and will be summarized using the appropriate SOC. These events will be summarized by severity and relationship to study drug for each treatment group.

12.7.4. Renal Safety

Baseline eGFR and values of CK will be summarized by treatment group and by baseline eGFR categories. Shift tables of eGFR category from baseline over the study will be provided by treatment group. Finally, muscle-related AEs will be summarized by treatment group and by baseline eGFR category.

